1.0 Introduction

This Statistical Analysis Plan (SAP) describes the statistical analyses for upadacitinib Study M19-051 'A Multicenter, Randomized, Double-Blind, Placebo-Controlled Dose-Ranging Study to Evaluate the Safety and Efficacy of Upadacitinib in Subjects with Non-Segmental Vitiligo.'

Study M19-051 examines the efficacy and safety of upadacitinib for the treatment of adult subjects with non-segmental vitiligo (NSV).

The analyses of pharmacokinetic endpoints and biomarkers will not be covered in this SAP.

The SAP will not be updated in case of administrative changes or amendments to the protocol unless the changes impact the analysis.

Unless noted otherwise, all analyses will be performed using SAS Version 9.4 (SAS Institute Inc., Cary, NC 27513) or later under the UNIX operating system.

2.0 Study Design and Objectives

2.1 Objectives, Hypotheses and Estimands

The primary objective of this study is to evaluate the safety and efficacy of upadacitinib for the treatment of adult subjects with NSV. The primary efficacy objective is based on the percent change from Baseline in Facial Vitiligo Area Scoring Index (F-VASI) at Week 24 with upadacitinib treatment compared to placebo in the Intent-to-Treat (ITT) Population, which consists of all randomized subjects.

The hypothesis corresponding to the primary endpoint is:

Percent change from Baseline in F-VASI with upadacitinib is greater than that with placebo at Week 24.

The estimand corresponding to the primary endpoint is defined as:

Difference in the percent change from Baseline in F-VASi at Week 24, regardless of treatment discontinuation, between each of the upadacitinib dose groups compared with placebo in the adult subjects with NSV.

2.2 Study Design Overview

This is a Phase 2, multicenter, randomized, double-blinded, parallel-group, placebo-controlled dose-ranging study that will evaluate the safety and efficacy of upadacitinib in adult subjects \geq 18 to 65 years of age with NSV. The study is comprised of a 35-day Screening Period, a 24-week double-blind treatment period (Period 1), a 28-week blinded long-term extension (Period 2), and a 30-day Follow-up Period.

Subjects who meet eligibility criteria at Baseline will be randomized in a 2:2:2:1:1 ratio to one of five treatment groups:

[figure not shown]
- Group 1: upadacitinib 22 mg once daily (QD) (N = 40) (Period 1) → upadacitinib 22 mg QD (Period 2)
- Group 2: upadacitinib 11 mg QD (N = 40) (Period 1) → upadacitinib 11mg QD (Period 2)
- Group 3: upadacitinib 6 mg QD (N = 40) (Period 1) → upadacitinib 6 mg QD (Period 2)
- Group 4: placebo (N = 20) (Period 1) → upadacitinib 22 mg QD (Period 2)
- Group 5: placebo (N = 20) (Period 1) → upadacitinib 11 mg QD (Period 2)

At Week 24, subjects who were randomized to placebo at Baseline will be switched to either upadacitinib 22 mg (Group 4) or upadacitinib 11 mg (Group 5) in a blinded fashion per pre-specified randomization assignments.

The AbbVie study team will be unblinded to perform the Week 24 primary analysis. The unblinding will take place after all subjects have completed the Week 24 visit or have prematurely discontinued prior to Week 24. Sites and subjects will remain blinded throughout the study.

The schematic of the study is shown in [Figure 1](#).

Figure 1. Study Schematic

BL = Baseline; F-VASI = Facial Vitiligo Area Scoring Index; PBO = placebo; QD = once daily; UPA = upadacitinib

2.3 Treatment Assignment and Blinding

All subjects will be assigned a unique identification number by the IRT at the screening visit. For subjects who rescreen, the screening number assigned by the IRT at the initial screening visit should be used. The IRT will assign a randomization number that will encode the subject's treatment group assignment according to the randomization schedule.

Subjects who meet eligibility criteria at Baseline will be randomized in a 2:2:2:1:1 ratio to one of the five treatment groups:

- Group 1: upadacitinib 22 mg QD (N = 40) (Period 1) → upadacitinib 22 mg QD (Period 2)
- Group 2: upadacitinib 11 mg QD (N = 40) (Period 1) → upadacitinib 11mg QD (Period 2)

- Group 3: upadacitinib 6 mg QD (N = 40) (Period 1) → upadacitinib 6 mg QD (Period 2)
- Group 4: placebo (N = 20) (Period 1) → upadacitinib 22 mg QD (Period 2)
- Group 5: placebo (N = 20) (Period 1) → upadacitinib 11 mg QD (Period 2)

Randomization will be stratified by the age group (≤ 50 and > 50), Baseline disease severity (T-VASI < 15 and ≥ 15), and status of active vitiligo (Yes/No) defined as follows:

- Active: Showing new lesions or progression (enlargement) of existing lesions within the last 6 months and/or presenting clinical subtypes indicative of progressing vitiligo (i.e., confetti-like depigmentation, trichrome pattern, or Koebner phenomenon).

At Week 24, subjects who were randomized to placebo at Baseline will be switched to either 22 mg (Group 4) or 11 mg (Group 5) upadacitinib in a blinded fashion per pre-specified randomization assignments.

2.4 Sample Size Determination

Assuming a Week 24 percent change from Baseline in F-VASI of 0% in the placebo arm, a conservative estimate based on a prior study in vitiligo,¹ the planned total sample size of 160 subjects (40 subjects in each upadacitinib group, 40 subjects in total in the placebo groups) will provide more than 90% power to detect the treatment difference of 40% reduction (assuming a standard deviation of 54.8%) in at least 1 upadacitinib group versus placebo using a 2-sided significance level of 0.1 based on the two-sample t-test.

3.0 Endpoints

3.1 Primary Endpoint

The primary endpoint is the percent change from Baseline in F-VASI at Week 24.

3.2 Secondary Endpoints

- Achievement of F-VASI 75 ($\geq 75\%$ improvement in F-VASI from Baseline) at Week 24;
- Achievement of F-VASI 50 ($\geq 50\%$ improvement in F-VASI from Baseline) at Week 24;
- Achievement of total Vitiligo Area Scoring Index (T-VASI) 50 ($\geq 50\%$ improvement in T-VASI from Baseline) at Week 24;
- Percent change from Baseline in T-VASI at Week 24;
- Change from Baseline in the vitiligo quality-of-life (VitiQoL) total score at Week 24.

3.3 Other Efficacy Endpoints

Additional Efficacy Endpoints include the primary and all secondary endpoints assessed at visits as noted in the Study Activities table (Protocol Appendix D), other than Week 24. Additional Efficacy Endpoints also include the following measurements assessed at visits as specified in the Study Activities table (Protocol Appendix D):

- Achievement of F-VASI 90 ($\geq 90\%$ improvement in F-VASI from Baseline);
- Achievement of T-VASI 75 ($\geq 75\%$ improvement in T-VASI from Baseline);
- Achievement of T-VASI 90 ($\geq 90\%$ improvement in T-VASI from Baseline);
- Mean and percent change from Baseline in the vitiligo extent score (VES);
- Achievement of vitiligo noticeability scale (VNS) score of "A lot less noticeable (4)" or "No longer noticeable (5)";
- Achievement of Dermatology Life Quality Index (DLQI) total score of "0" or "1";
- Change from Baseline in the Hospital Anxiety and Depression Scale (HADS) anxiety and depression scores;
- Proportion of subjects selecting each of the response categories of VitiQoL 16 questions;

- Achievement of Physician's Global Impression of Change-Vitiligo (PhGIC-V) of "Much better (1)" or "A little better (2);"
- Achievement of Patient's Global Impression of Change-Vitiligo (PaGIC-V) of "Much better (1)" or "A little better (2);"
- Achievement of Face – Physician Global Vitiligo Assessment (F-PhGVA) of "No depigmentation (0)" or "Limited extent of depigmentation (1);"
- Achievement of Total – Physician Global Vitiligo Assessment (T-PhGVA) of "No depigmentation (0)" or "Limited extent of depigmentation (1);"
- Achievement of Face – Patient Global Vitiligo Assessment (F-PaGVA) of "No depigmentation (0)" or "Limited extent of depigmentation (1);"
- Achievement of Total – Patient Global Vitiligo Assessment (T-PaGVA) of "No depigmentation (0)" or "Limited extent of depigmentation (1)."'

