### 3.4 Additional Endpoints

---

Additional Efficacy Endpoints include the primary and all secondary endpoints assessed at visits as noted in the Activity Schedule ([Appendix D](#)), other than Week 24. Additional Efficacy Endpoints also include the following measurements assessed at visits as specified in the Activity Schedule:

- Achievement of F-VASI 90 ( $\geq 90\%$  improvement in F-VASI from Baseline);
- Achievement of T-VASI 75 ( $\geq 75\%$  improvement in T-VASI from Baseline);
- Achievement of T-VASI 90 ( $\geq 90\%$  improvement in T-VASI from Baseline);
- Mean and percent change from Baseline in the vitiligo extent score (VES);
- Achievement of vitiligo noticeability scale (VNS) score of "A lot less noticeable (4)" or "No longer noticeable (5)";
- Dermatology Life Quality Index (DLQI) total score of "0" or "1";
- Change from Baseline in the Hospital Anxiety and Depression Scale (HADS) scores;
- Proportion of subjects selecting each of the response categories of VitiQoL 16 questions;
- Achievement of Physician's Global Impression of Change-Vitiligo (PhGIC-V) of "Much better (1)" or "A little better (2)";
- Achievement of Patient's Global Impression of Change-Vitiligo (PaGIC-V) of "Much better (1)" or "A little better (2)";
- Achievement of Face – Physician Global Vitiligo Assessment (F-PhGVA) of "No depigmentation (0)" or "Limited extent of depigmentation (1)";
- Achievement of Total – Physician Global Vitiligo Assessment (T-PhGVA) of "No depigmentation (0)" or "Limited extent of depigmentation (1)";
- Achievement of Face – Patient Global Vitiligo Assessment (F-PaGVA) of "No depigmentation (0)" or "Limited extent of depigmentation (1)";
- Achievement of Total – Patient Global Vitiligo Assessment (T-PaGVA) of "No depigmentation (0)" or "Limited extent of depigmentation (1)."

Details on efficacy variables are provided in the operations manual ([Appendix F](#)).

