#### Disease/Condition Activity

- 3. Documented clinical diagnosis of NSV.
- 4. At Screening and Baseline visits, subjects must have  $\geq 0.5$  F-VASI AND  $\geq 5$  T-VASI.
- 5. No segmental or localized vitiligo.

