4.0 Analysis Populations

The following Intent-to-Treat (ITT) populations will be used for the analyses.

- The ITT Population in Period 1 (ITT_1) includes all randomized subjects in Period 1. Subjects will be included in the analysis according to the treatment groups that they are randomized to. Analyses will include the following 4 groups: upadacitinib (UPA) 22 mg QD, UPA 11 mg QD, UPA 6 mg QD and placebo.
- The ITT Population in Period 2 (ITT_2) includes all subjects entered Period 2. Subjects will be included in the analysis according to the 5 treatment groups that they are randomized to at baseline: UPA 22 mg QD-> UPA 22 mg QD, UPA 11 mg QD-> UPA 11 mg QD, UPA 6 mg QD-> UPA 6 mg QD, Placebo-> UPA 22 mg QD and Placebo-> UPA 11 mg QD.

- The ITT_1/ITT_2 Populations will be used for all efficacy analyses across Period 1/Period 2.

The following three Safety Populations will be used for the safety analysis:

- The Safety Population in Period 1 (Safety_1) is defined as all subjects who are randomized and received at least one dose of study drug in Period 1. Subjects will be summarized in the following 4 groups: UPA 22 mg QD, UPA 11 mg QD, UPA 6 mg QD and placebo, based on the treatment actually received (defined as the most frequent dose regimen received in Period 1).
- The Safety Population in Period 2 (Safety_2) is defined as all subjects received at least one dose of study drug in Period 2. Subjects will be included in the 5 groups same as which they were randomized to at baseline: UPA 22 mg QD-> UPA 22 mg QD, UPA 11 mg QD-> UPA 11 mg QD, UPA 6 mg QD-> UPA 6 mg QD, Placebo-> UPA 22 mg QD and Placebo-> UPA 11 mg QD.
- The all upadacitinib treated (ALL_UPA) Population is defined as subjects who received at least one dose of upadacitinib in the study. Subjects will be analyzed based on the treatment actually received: UPA 22 mg QD, UPA 11 mg QD and UPA 6 mg QD.

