9.5 Additional Efficacy Analyses

In Period 1, unless otherwise specified, additional efficacy endpoints will be compared between the each upadacitinib treatment group and placebo. The categorical endpoints and continuous endpoints will be analyzed by CMH and MMRM, respectively, and the analyses are specified in Section 9.1 and Section 9.2. Proportion of subjects selecting each of the 16 VitiQoL questions will be summarized for each of the 16 questions by response categories at each visit as observed.

In Period 2, the categorical endpoints will be summarized by treatment groups as observed, and the continuous endpoints will be analyzed as observed using ANCOVA as described in Table 1. The analyses are specified in Section 9.1 and Section 9.2.

In Addition, at the time of the Primary Analysis, additional long-term analysis up to Week 52 will be provided for the below variables among all subjects who may potentially reach to Week 52 by the data cutoff using NRI-MI (categorical variables) or MMRM (continuous variables):

- F-VASI 50, F-VASI 75,
- T-VASI 50,
- Percent change from Baseline in F-VASI,
- Percent change from Baseline in T-VASI

At the time of the final analysis, the above variables will be evaluated up to Week 52 using NRI-MI (categorical variables) or MMRM for the continuous variables.

In addition, for VitiQoL, VNS, DLQI and HADS, analyses will be performed, for up to Week 52, for the following:

- Change from Baseline in VitiQoL question 16 regarding the severity of skin condition.
- Proportion of subjects selecting each of the response categories of VNS
- Change from Baseline in Dermatology Life Quality Index (DLQI) total score
- Achievement of a clinically meaningful improvement in DLQI total score defined as $\Delta \text{DLQI} \geq 4$ (for subjects with $\text{DLQI} \geq 4$ at baseline)
- Achievement of a clinically meaningful improvement in HADS anxiety and depression scores defined as $\Delta \text{HADS} \geq 1.5$ (for subjects with $\text{HADS} \geq 1.5$ at baseline)

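### DLQI 0/1 and the four global-assessment 0/1 endpoints count subjects already at 0/1 at Baseline as achievers, so they mix reaching that level with staying there

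*SAP*

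**What the plan says.** - **Definition.** SAP 3.3 defines "Achievement of Dermatology Life Quality Index (DLQI) total score of" 0 or 1, and "Achievement of Face – Physician Global Vitiligo Assessment (F-PhGVA) of" 0 or 1. T-PhGVA, F-PaGVA and T-PaGVA follow the same pattern. Protocol 3.4 matches, with "Dermatology Life Quality Index (DLQI) total score of" 0 or 1. None of the five carries a Baseline condition or requires an improvement.
- **Analysis set.** SAP 4.0: "The ITT_1/ITT_2 Populations will be used for all efficacy analyses across Period 1/Period 2". ITT_1 is every randomized subject. Protocol 7.2 has the same all-ITT rule.
- **Method.** SAP 9.5: "The categorical endpoints and continuous endpoints will be analyzed by CMH and MMRM, respectively". The CMH strata in SAP 9.1 are age group, T-VASI group and active vitiligo; the Baseline level of the scale being analysed is not among them.
- **Entry.** Protocol 5.1: "At Screening and Baseline visits, subjects must have" F-VASI of at least 0.5 and T-VASI of at least 5. There is no floor on DLQI or on any global assessment.
- **Contrast.** SAP 9.5 has a second DLQI responder, "Achievement of a clinically meaningful improvement in DLQI total score defined as" a change of at least 4, limited to subjects with Baseline DLQI of at least 4. The HADS responder is limited in the same way, at 1.5.
- **Data.** All five scales are assessed at Baseline (Protocol Appendix D), and SAP 7.1 tabulates their Baseline values as categorical variables.

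**The concern.** The endpoints are called achievement, but the rule measures status. A subject with DLQI 1 at Baseline and DLQI 1 at Week 24 is an achiever, as is a subject whose face was rated at level 1 (limited depigmentation) on both occasions. Neither has changed.

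Entry does not prevent this. SAP Appendix E gives F-VASI a range of 0 to 100, so a facial floor of 0.5 is low, and nothing bars a Baseline DLQI of 0 or 1. On the two physician scales the VASI floors effectively exclude level 0, so there the question is level 1.

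Two things are at stake. The reported proportion combines subjects who reached 0/1 with subjects who never left it. And in a dose-ranging study with 40 per group, unchanged subjects raise the rate in every arm and can compress the separation between doses and placebo.

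**Working it through.** **The plan's own figure.** The only stated power is for the primary endpoint (SAP 2.4): more than 90% for a 40-point difference, SD 54.8, 40 per group, two-sided 0.1. Check: 40 / (54.8 × √(2/40)) = 40 / 12.25 = 3.26; 3.26 − 1.645 = 1.62; power 94.7% (normal), 94.4% (noncentral t, 78 df). It reproduces and is not affected by this point. The documents give no power for the five 0/1 endpoints.

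**Model.** Let b be the share at 0/1 at Baseline, p the response rate among the others, and r the share of Baseline 0/1 subjects counted as 0/1 at the visit.

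- Arm proportion: P = b·r + (1 − b)·p
- All-randomized difference: D = (1 − b)·(p_U − p_P) + b·(r_U − r_P)

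With equal retention the second term is zero and D is (1 − b) times the difference among subjects who could newly achieve. D is smaller than that difference whenever r_U − r_P is smaller than p_U − p_P.

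**Assumptions, not in the documents.** p_P = 10%, p_U = 35% (25 points); b from 10% to 40%; r as shown. From the documents: 40 per arm (placebo pooled) and two-sided 0.1. Power is the unstratified two-proportion normal approximation with pooled variance under the null. The restricted analysis has 40(1 − b) per arm.

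**One case in full: b = 30%, retention 95% in both arms.**
- Placebo: 0.30 × 0.95 + 0.70 × 0.10 = 35.5%
- Upadacitinib: 0.30 × 0.95 + 0.70 × 0.35 = 53.0%
- Difference 17.5 points. Null SE = √(0.4425 × 0.5575 × 2/40) = 0.1111; alternative SE = √((0.355 × 0.645 + 0.53 × 0.47)/40) = 0.1093. Power = Φ((0.175 − 1.645 × 0.1111)/0.1093) = 47%.
- Restricted: 25 points, 28 per arm, power 73%.

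**Difference in points (power), all randomized, by retention on placebo / upadacitinib:**

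| b | 95% / 95% | 75% / 95% | 65% / 95% | Restricted, n per arm |
|---|---|---|---|---|
| 10% | 22.5 (72%) | 24.5 (79%) | 25.5 (82%) | 25 (83%), 36 |
| 20% | 20.0 (58%) | 24.0 (73%) | 26.0 (80%) | 25 (78%), 32 |
| 30% | 17.5 (47%) | 23.5 (69%) | 26.5 (79%) | 25 (73%), 28 |
| 40% | 15.0 (38%) | 23.0 (67%) | 27.0 (79%) | 25 (67%), 24 |

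With b = 0, power is 86% either way. When retention is equal, its level matters little: at 80% or 100% in both arms, all-randomized power moves by at most about 1.5 points from the first column. The gap in retention between arms matters a great deal.

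**The case against.** **Dilution is not established.** A reader might infer that the plan loses power on these endpoints. That needs subjects at 0/1 at Baseline, and the documents give no distribution for any of the five scales. It also needs retention to be similar across arms, and the plan allows for worsening: active disease is a stratification factor, and Protocol 5.5 has a discontinuation rule based on T-VASI increase. Placebo subjects may leave level 1 more often. At 75% vs 95% the power gap is only about 1 to 5 points; at 65% vs 95% restriction loses power from 20% prevalence upward. This stands.

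**Baseline DLQI 0/1 may be uncommon.** Protocol 4.2 calls vitiligo generally asymptomatic, which might be read as showing that many subjects enter at DLQI 0/1. The same sentence says quality of life is significantly impaired, so it does not support that reading.

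**The total scales are less exposed.** The T-VASI floor of 5 makes level 1 less evident on T-PhGVA and T-PaGVA. The available text does not map VASI to global-assessment levels, and the operations manual, which the Protocol cites for details of the efficacy variables, was not available. This stands.

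**Baseline status will be visible.** SAP 7.0 and 7.1 tabulate it by arm, and change-based companions exist (DLQI change, VASI 50/75/90, the global impressions of change). So it would be too strong to say that a reader cannot see Baseline status. What is missing is the link, subject by subject, between Baseline and visit status.

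**The SAP 9.5 restrictions solve a different problem.** They remove subjects for whom the target is arithmetically impossible, whereas anyone can be at 0/1, and staying there is a legitimate outcome. This is fair, but it does not make staying at 0/1 the same as reaching it, and DLQI still has one responder with a Baseline condition and one without, unexplained.

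**No bias.** Randomization keeps the all-randomized comparison valid under the null. Nothing here suggests an inflated type I error.

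**Conclusion.** The point holds as a matter of definition and interpretation: for five additional endpoints, an unchanged subject can count as an achiever, and no provision in the Protocol or SAP excludes such subjects, requires improvement, or adjusts for the Baseline level of the scale.

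Loss of sensitivity is conditional. With similar retention in both arms the difference shrinks in proportion to the Baseline 0/1 share; in the illustration all-randomized power is 72% to 38%, against 83% to 67% restricted, at 10% to 40% prevalence. With a retention gap as large as the response difference (25 points here) there is no dilution. Prevalence, response rates and retention are all assumed, and the true size is unknown. It is likelier to matter for DLQI and the facial scales than for the total scales.

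This is an inexpensive improvement, not a flaw in the main inference. These endpoints have no stated power and no multiplicity control, and the primary and secondary endpoints are untouched. VNS, PhGIC-V and PaGIC-V are outside the point, since they rate change and have no Baseline assessment.

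**What to change.** In SAP 3.3 and 9.5:
- Analyse DLQI 0/1 in subjects with Baseline DLQI above 1, and each of F-PhGVA, T-PhGVA, F-PaGVA and T-PaGVA 0/1 in subjects with a Baseline score of at least 2 on that scale.
- Keep the all-randomized result alongside.
- Report, per arm and per scale, the number at 0/1 at Baseline.

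In SAP 4.0, state this as an exception to the all-ITT rule, and note that it departs from the same rule in Protocol 7.2.

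**Cost.** SAP wording and a few extra table columns; no new data. The subset is defined by a Baseline value, so the comparison within it remains randomized. The price is smaller denominators and sparser CMH strata. At 40% prevalence, 24 per arm leaves 48 subjects per comparison across 2 × 2 × 2 = 8 strata, an average of 6 per stratum, which the unstratified power figures do not reflect. That is one more reason to show both versions.

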3.4 Safety Endpoints

Safety evaluations include AEs, serious adverse events (SAEs), adverse events of special interest (AESIs), AEs leading to discontinuation, vital signs, laboratory tests (hematology, chemistry, liver function tests), and physical examination.

4.0 Analysis Populations

The following Intent-to-Treat (ITT) populations will be used for the analyses.

- The ITT Population in Period 1 (ITT_1) includes all randomized subjects in Period 1. Subjects will be included in the analysis according to the treatment groups that they are randomized to. Analyses will include the following 4 groups: upadacitinib (UPA) 22 mg QD, UPA 11 mg QD, UPA 6 mg QD and placebo.
- The ITT Population in Period 2 (ITT_2) includes all subjects entered Period 2. Subjects will be included in the analysis according to the 5 treatment groups that they are randomized to at baseline: UPA 22 mg QD-> UPA 22 mg QD, UPA 11 mg QD-> UPA 11 mg QD, UPA 6 mg QD-> UPA 6 mg QD, Placebo-> UPA 22 mg QD and Placebo-> UPA 11 mg QD.

- The ITT_1/ITT_2 Populations will be used for all efficacy analyses across Period 1/Period 2.

The following three Safety Populations will be used for the safety analysis:

- The Safety Population in Period 1 (Safety_1) is defined as all subjects who are randomized and received at least one dose of study drug in Period 1. Subjects will be summarized in the following 4 groups: UPA 22 mg QD, UPA 11 mg QD, UPA 6 mg QD and placebo, based on the treatment actually received (defined as the most frequent dose regimen received in Period 1).
- The Safety Population in Period 2 (Safety_2) is defined as all subjects received at least one dose of study drug in Period 2. Subjects will be included in the 5 groups same as which they were randomized to at baseline: UPA 22 mg QD-> UPA 22 mg QD, UPA 11 mg QD-> UPA 11 mg QD, UPA 6 mg QD-> UPA 6 mg QD, Placebo-> UPA 22 mg QD and Placebo-> UPA 11 mg QD.
- The all upadacitinib treated (ALL_UPA) Population is defined as subjects who received at least one dose of upadacitinib in the study. Subjects will be analyzed based on the treatment actually received: UPA 22 mg QD, UPA 11 mg QD and UPA 6 mg QD.

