10.2.3 Treatment-Emergent Adverse Events by SOC and/or PT

Treatment-emergent adverse events will be summarized by SOC and PT; by maximum relationship to study drug as assessed by the investigator (e.g., reasonable possibility or no reasonable possibility) and SOC and PT; by maximum toxicity and SOC and PT; by relationship to COVID-19 and SOC and PT; by $\geq 5\%$ subjects in any treatment group by SOC and PT. The number and percentage of subjects experiencing TEAEs will be provided for these summaries in the Safety_1 and ALL_UPA Populations. Number of TEAEs per 100 patient-years of exposure will be summarized by SOC and PT for the Safety 1 and All_UPA Populations. Specific adverse events will be counted once for each subject for calculating percentages, unless stated otherwise. In addition, if the same adverse event occurs multiple times within a subject, the highest toxicity and level of relationship to investigational product will be reported.

In addition, treatment-emergent adverse events will be summarized by PT and sorted by decreasing frequency for the total active treatment group.

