10.3 Analysis of Laboratory Data

Data collected from central and local laboratories, including additional laboratory testing due to an SAE, will be used in all analyses, except for Baseline where SAE-related laboratory assessments on or before the first dose of study drug will be excluded. The clinical laboratory tests defined in the protocol operations manual (e.g., hematology and clinical chemistry) will be summarized.

Raw values and change from Baseline (percent change if applicable) to each applicable post-baseline visit will be summarized for selected laboratory variables in the Safety_1 and Safety_2 Populations. The following descriptive statistics will be presented by treatment groups: number of observations, Baseline mean (Standard deviation, SD), visit mean (SD), medium, change from Baseline mean (SD), standard error, and the 95% confidence interval of the mean change from Baseline.

Percent change from Baseline in LDL-C, HDL-C, total cholesterol and ratio of LDL-C to HDL-C will also be summarized similarly in the Safety_1 and Safety_2 Populations.

For the Safety_1 and ALL_UPA Populations:

A shift table from baseline to the worse post-baseline value (based on NCI CTC criteria) during treatment will be created. A similar shift table will be provided to summarize shifts from baseline to the final post-baseline value. The number and percentage of subjects will be summarized.

Laboratory abnormalities will be evaluated based on Potentially Clinically Important (PCI) criteria ([Appendix C](#)). For each laboratory PCI criterion, the number and percentage of subjects who have a laboratory value meeting the criteria will be summarized. Listings will be provided to summarize subject-level laboratory data for subjects meeting PCI criteria.

For the purpose of assessing for potential Hy's law cases, the frequencies and percentages of subjects with post-baseline liver specific function test values that meet PCI criteria ([Appendix C](#)) of potential clinical interest should be presented.

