10.4 Analysis of Vital Signs

Vital sign measurements of systolic and diastolic blood pressure, heart rate, respiratory rate, and body temperature will be summarized.

Each vital sign variable will be summarized for all time points (starting with Baseline) with the number of non-missing observations, mean and standard deviation, median, minimum and maximum. Change from Baseline to each applicable post-baseline visit will be summarized for each vital sign variable, with the number of observations, Baseline mean, and visit mean. Mean, standard error, and 95% confidence interval will be presented for the change from Baseline within each treatment group in Safety_1 and Safety_2 Populations.

Vital sign variables will be evaluated based on PCI criteria ([Appendix C](#)) for the Safety_1 and ALL_UPA Populations. For each vital sign PCI criterion, the number and percentage of subjects who have a vital sign value meeting the criteria will be summarized. Listings

will be provided to summarize subject-level vital sign data for subjects meeting PCI criteria.

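### Beyond Week 24, the ALL_UPA laboratory and vital-sign percentages compare 11 mg and 22 mg with 6 mg on unequal exposure

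*SAP*

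**What the plan says.** SAP 4.0 sets membership: "The all upadacitinib treated (ALL_UPA) Population is defined as subjects who received at least one dose of upadacitinib in the study". It then sets the columns: "Subjects will be analyzed based on the treatment actually received: UPA 22 mg QD, UPA 11 mg QD and UPA 6 mg QD".

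SAP 2.2 sends the two placebo groups, 20 subjects each, to 22 mg and 11 mg at Week 24. No placebo group feeds 6 mg. The protocol synopsis gives the planned exposure that follows: 52 weeks at 6 mg, and either 28 or 52 weeks at 11 mg and 22 mg.

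For Safety_1 and ALL_UPA, SAP 10.3 plans laboratory shift tables (to the worst and to the final value) and laboratory PCI tables. For each laboratory PCI criterion, "the number and percentage of subjects who have a laboratory value meeting the criteria will be summarized". SAP 10.4 does the same for vital signs: "the number and percentage of subjects who have a vital sign value meeting the criteria will be summarized". Neither section specifies a patient-year rate, a common time window or a split by length of exposure. SAP 10.2 does plan events per 100 patient-years, but for adverse events only.

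**The concern.** A table of subjects who ever had a qualifying value, or of each subject's worst value, depends on how long subjects are observed. In ALL_UPA one third of the 11 mg and 22 mg columns has about half the planned time on drug of the rest, and nobody in the 6 mg column does. A percentage that looks the same at 6 mg and 22 mg could therefore hide a higher risk per unit time at 22 mg.

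Safety is part of the primary objective and the study is dose-ranging. Protocol 2.2 names transaminases, lipids, creatine phosphokinase, hemoglobin and white cells as laboratory values known to change on upadacitinib. Safety_1 ends at Week 24, and Safety_2 has no PCI or shift tables, so ALL_UPA is the only place where PCI and worst-value results extend past Week 24.

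**Working it through.** **Inputs.** 160 subjects randomized 2:2:2:1:1; Period 1 of 24 weeks and Period 2 of 28 weeks (SAP 2.2, 2.4). Visits are from Protocol Appendix D.

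**The plan's own figures.** 160 × 2/8 = 40 and 160 × 1/8 = 20, which gives 40/40/40/20/20. Subjects on drug from Day 1 have 24 + 28 = 52 weeks; switchers have 28. Both match the documents.

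**Planned exposure by ALL_UPA column, full retention.**
- 22 mg and 11 mg, each: 60 subjects; mean (40 × 52 + 20 × 28)/60 = 44 weeks; 60 × 44 × 7/365.25 = 50.6 patient-years.
- 6 mg: 40 subjects; mean 52 weeks; 40 × 52 × 7/365.25 = 39.9 patient-years.
- Scheduled hematology and chemistry visits after starting upadacitinib: 10 from Day 1, 4 for switchers. The mean is (40 × 10 + 20 × 4)/60 = 8.0 at the two higher doses against 10 at 6 mg.

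**Effect on a percentage.** Let F(t) be the risk of a first qualifying value within t weeks on drug, the same at every dose, counting only values on upadacitinib. Then

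pooled percentage = (40 × F(52) + 20 × F(28))/60.

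The documents give no onset times, so F is an assumption. Its extremes are:
- All first occurrences by week 28: F(28) = F(52), so there is no understatement.
- All after week 28: F(28) = 0, so the pooled figure is 40/60 of the true one, 33% too low (10% shows as 6.7%).

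Under constant hazard and no dropout, F(28) = 1 − (1 − p)^(28/52), where p = F(52):

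| True 52-week risk p | F(28) | Pooled 11 or 22 mg | Relative shortfall |
|---|---|---|---|
| 5% | 2.7% | 4.2% | 15.2% |
| 10% | 5.5% | 8.5% | 14.9% |
| 20% | 11.3% | 17.1% | 14.5% |
| 40% | 24.1% | 34.7% | 13.3% |

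**Early onset.** If half of a 10% risk falls in the first 12 weeks and the rest is spread evenly, F(28) = 10% × (0.5 + 0.5 × 16/40) = 7.0%, and the pooled figure is (2 × 10% + 7.0%)/3 = 9.0%.

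**Masking.** Under constant hazard, a true 52-week risk of 11.75% at 22 mg shows as 10.0%, the same as a true 10% at 6 mg. The hazard ratio is ln(0.8825)/ln(0.90) = 1.19.

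**Dropout.** With an assumed 20% dropout by Week 52 and p = 10%, the figures are 9.0% at 6 mg and 7.8% at the higher doses. For dropout of 10% to 40%, the ratio of mean exposures is 0.86 to 0.89 and the direction is unchanged.

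**Against sampling error.** At 10%, the standard error of a 60-versus-40 difference is √(0.1 × 0.9 × (1/60 + 1/40)) = 6.1 points. The bias under constant hazard is about 1.5 points.

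**Change-from-Baseline criteria.** SAP 9.1 takes Baseline before the first study drug, and SAP section 10 gives no separate baseline for switchers. Read that way, a switcher's change in weight, blood pressure or pulse (Table C-4) includes 24 weeks on placebo. That can add qualifying subjects as well as remove them, so the direction cannot be stated.

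**The case against.** The best defence is that ALL_UPA is descriptive. Protocol 7.2 presents it as a comprehensive safety summary, no between-dose safety test is planned, and Safety_1 gives the same tables over an equal 24 weeks with a placebo column. SAP 6.0 reports duration by dose, so the imbalance will be visible, and subjects meeting PCI criteria are listed. Safety_2 already keeps the two switcher groups apart, with laboratory and vital-sign values by visit.

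There is also a partial exposure-adjusted counterpart. Protocol 6.1 makes a laboratory abnormality an adverse event if it meets the toxicity criteria in Protocol 6.2. The Table 3 cut-offs there for hemoglobin, neutrophils, lymphocytes and white cells match those in SAP Table C-1. Anemia, neutropenia, lymphopenia, hepatic disorder and renal dysfunction are events of special interest with patient-year rates in ALL_UPA (SAP 10.2.5).

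Much of this stands and limits the weight of the point. It does not close the gap. Safety_1 says nothing past Week 24, Safety_2 carries no PCI or shift table, a duration table does not correct a percentage, and the adverse-event overlap leaves out unconfirmed values, platelets, lipids and most vital-sign findings.

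A reader might extend the point to the TEAE tables by toxicity grade and by relationship, since SAP 10.2.3 says "The number and percentage of subjects experiencing TEAEs will be provided for these summaries in the Safety_1 and ALL_UPA Populations". The documents do not support that. SAP 10.2.2 gives patient-year rates in ALL_UPA for severe and for related TEAEs, and 10.2.3 adds rates by SOC and PT. Nor does the mechanism reach the final-value shift table: one last value per subject gives no extra chances to qualify.

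**Conclusion.** The point holds for three sets of ALL_UPA tables: laboratory PCI, worst-value laboratory shift and vital-sign PCI. It holds only for contrasts of 11 mg or 22 mg with 6 mg. For criteria that turn on the value itself, and with equal risk per time on drug, the higher-dose percentage is understated by 0% to 33% in relative terms. It is about 15% at a 10% risk if the hazard is constant and nobody drops out. This is small beside the sampling error of any one criterion, but it runs the same way across value-based criteria.

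Two stronger readings are tempting. One is that ALL_UPA obscures dose-related increases in general; it does not, because the 11 mg and 22 mg columns have the same 40 + 20 make-up and their contrast is balanced. The other is that understatement is certain for every criterion, weight gain included; the Baseline definition leaves the direction open for criteria based on change.

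**What to change.** In SAP 10.3 and 10.4, for ALL_UPA:

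1. In the PCI and worst-value shift tables, use the three groups on upadacitinib from Day 1 as the by-dose columns. Put placebo to 22 mg and placebo to 11 mg in their own columns and keep a pooled total. The five group labels already exist for Safety_2.
2. For each PCI criterion, add the number of subjects with a first qualifying value per 100 patient-years at risk, in the same columns. The rate should accompany the split, not replace it, because a pooled rate is even-handed only if the hazard is constant. In the early-onset example the crude pooled figures are 9.0/44 = 0.205 against 10.0/52 = 0.192 per 100 subject-weeks, which errs the other way.
3. For switchers, define baseline in ALL_UPA as the last value before the first upadacitinib dose.

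No new data are needed: two extra columns, one rate per PCI row and a sentence on baseline. The price is that the 11 mg and 22 mg by-dose columns hold 40 subjects instead of 60.
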